7.5.2 Clinical Laboratory Evaluation

The baseline visit is the last measurement taken prior to initial study drug administration. Quantitative clinical laboratory variables, i.e. hematology, biochemistry, and urinalysis will be summarized using descriptive statistics for each treatment group at each visit and at the End of Treatment. Additionally, a within-subject change will be calculated as the post-baseline measurement minus the baseline measurement and summarized in the same way.

Each laboratory result will be classified as low (L), normal (N), or high (H) at each visit according to the laboratory supplied reference ranges. The number and percentage of subjects below and above reference range will be summarized for each treatment group at each visit and at the End of Treatment.

Frequency tabulations of qualitative clinical laboratory variables (urinalysis) will be presented for each treatment group at each visit and at the End of Treatment.

For hematology and biochemistry, shift tables of reference range changes from baseline to Week 12 and End of Treatment will be presented for each treatment group. For urinalysis (qualitative), shift table will also be presented for each treatment group in the same way.

For coagulation, only listing will be presented for each treatment group.

The following data will be presented graphically by treatment group:

- Laboratory test results using box plot,
- Change from baseline in laboratory test results using box plot,
- Qualitative laboratory test results using bar chart,
- Shift scatter plot of maximum laboratory test results on treatment versus baseline,
- Laboratory test results using spaghetti plot.

All laboratory parameter's unit for analysis will be used Japan original unit. If there would be some gap between Korean unit and Japan unit, transpose to Japan original unit to use analysis.

7.5.2.1 Liver Enzymes and Total Bilirubin

The following potentially clinically significant criteria for liver tests – defined as Alkaline Phosphatase (ALP), Alanine Transaminase (ALT), total bilirubin, Aspartate Transaminase (AST) and their combination are defined. The subject's highest value during the investigational period will be used.

Parameter	Criteria
ALT	> 3xUpper limit of normal (ULN) > 5xULN > 10xULN > 20xULN
AST	> 3xULN > 5xULN > 10xULN

	> 20xULN
ALT or AST	> 3xULN
Total Bilirubin	> 2xULN
ALP	> 1.5xULN
ALT and/or AST AND Total Bilirubin ^(*)	(ALT and/or AST > 3xULN) and total bilirubin > 2xULN

^(*) Combination of values measured within same sample

The number and percentage of subjects with potentially clinically significant values in liver enzyme and total bilirubin tests during the investigational period will be presented by treatment group.

7.5.3 Vital Signs

The baseline visit is the last measurement taken prior to initial study drug administration.

Vital signs were measured during each visit at the clinical site. In addition, patients were required to measure vital signs for 3 days prior to the visit at home, both in the morning and in the afternoon.

7.5.3.1 Vital signs (at the clinical site)

Vital signs (systolic blood pressure, diastolic blood pressure, and pulse rate) at the clinical site will be summarized using descriptive statistics by treatment group and at each visit and at the End of Treatment. Additionally, a within-subject change will be calculated per visit as the post-baseline measurement minus the baseline measurement and summarized by treatment group and at each visit and at the End of Treatment.

Following data will be presented graphically by treatment group:

- Vital sign results using mean (+/- 95% CI) plot,
- Change from baseline in vital sign results using mean (+/- 95% CI) plot,
- Shift scatter plot of maximum vital sign results on treatment versus baseline.

7.5.3.2 Vital signs (at home)

Vital signs (systolic blood pressure, diastolic blood pressure, and pulse rate) at home will be summarized using descriptive statistics by treatment group and at each visit and at the End of Treatment. Additionally, a within-subject change will be calculated per visit as the post-baseline measurement minus the baseline measurement and summarized by treatment group and at each visit and at the End of Treatment.

Following data will be presented graphically by treatment group:

- Vital sign results using mean (+/- 95% CI) plot,
- Change from baseline in vital sign results using mean (+/- 95% CI) plot,
- Shift scatter plot of maximum vital sign results on treatment versus baseline.

The value for using table and figure are the average of results for 3 days prior to the visit at home, both waking up and bedtime. And the value for using listing is the average of results for 3 days prior to the visit at home by waking up and bedtime.

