1.4.1.3 Clinically significant adverse drug reactions with mirabegron treatment

Identified risks with mirabegron treatment include increased heart rate and tachycardia as well as hypersensitivity reactions. Potential risks include QT prolongation, increased

blood pressure, UTI, urinary retention, fetal disorders after exposure during pregnancy, and events induced by increased exposure to CYP2D6 substrates. The risks of QT prolongation, increased heart rate, or increased blood pressure are greater with increasing exposure at supratherapeutic doses, and can be mitigated with optimal dose selection. The maximum therapeutic dose of mirabegron, based on the overall benefit-risk is 50 mg once daily. In patients with severe renal impairment or moderate hepatic impairment, the dose of mirabegron is 25 mg once daily. Further dose adjustments for renal impairment, hepatic impairment and concomitant use of strong CYP3A4 inhibitors may be required.

Overall, mirabegron at the therapeutic oral doses of 25 mg and 50 mg once daily is considered to be a safe and effective for the treatment of adult patients with OAB. The benefits of treatment exceed the risk associated with the use of the product. Mirabegron was approved in Japan in 2011, and to date has been approved in more than 50 countries, including the United States and European Union.

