5.1.5 Restrictions During the Study

(1) Medication

When prescribing the study medication, the Investigator or Sub-investigator will explain to the subjects how to take the study medication, with emphasis on the following:

- The subject should take the study medication with water, once daily after breakfast.
- The subject should start taking the prescribed study medication on the day following dispensing of the study drug(s).
- The subject should return any unused study medication at the next visit, and report their compliance to the Investigator or Sub-investigator.
- If the subject has discontinued taking the study medication at his/her own discretion, he/she must visit the study site at the earliest possible time to undergo examination by the Investigator or Sub-investigator.

(2) Micturition diary

The Investigator or Sub-investigator will provide each subject with a micturition diary, after entering into the diary the date of the next scheduled visit, the dates on which the diary should be completed, and the subject number. When providing the micturition diary to the subject, the Investigator or Sub-investigator will explain to the subject how to complete the micturition diary, with emphasis on the following:

- As a rule, the subject will complete the micturition diary during the 3 days immediately before each of the scheduled visits (i.e., at Visits 2, 3, 4, and 5/End of Treatment. Each diary day starts at 06:00 and ends at 05:59 on the following day.
- For the 3 days of recording in the micturition diary, the subject will record their awakening and bedtime hours; time of each micturition; number of micturition episodes, urgency episodes, urinary incontinence episodes, voided volume, sitting blood pressure (SBP and DBP) and pulse rate with the times of measurements. In addition, the subject will record the time of medication. Voided volume will be recorded at Visits 2, and 5 only.
- Sitting blood pressure and pulse rate will be measured twice consecutively on awakening and before bedtime. The second measured value will be recorded in the patient diary. When measurements on awakening are not possible, these should be taken before taking medication for the day as far as possible.
- The subject should bring their completed micturition diary to the next visit.

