7.10.1 Missing Data

The final handling of missing data will be decided by the time of database lock, and will be based on the opinion and advice of a medical expert.

As a general principle, no imputation of missing data for other variables will be done. Exceptions are the start and stop dates of AEs and concomitant medication.

The imputed dates will be used to allocate the concomitant medication and AEs to a treatment group, in addition to determining whether an AE is/is not treatment emergent. Listings of the AEs and concomitant medications will present the actual partial dates; imputed dates will not be shown.

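### Home blood pressure and pulse summaries pool awakening (pre-dose) and bedtime (post-dose) readings, so they cannot show whether an effect differs by time of day and can dilute one that is larger at bedtime

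*SAP*

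**What the plan says.** Protocol 5.1.5 sets the home schedule for the three diary days before Visits 2 to 5: "Sitting blood pressure and pulse rate will be measured twice consecutively on awakening and before bedtime", with the second of each pair recorded. That gives two recorded values per day and six per diary. The same section fixes dosing: "The subject should take the study medication with water, once daily after breakfast". It protects the timing of the first reading: "When measurements on awakening are not possible, these should be taken before taking medication for the day as far as possible". Subjects also record the times of measurement and of medication.

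SAP 7.5.3.2 then defines the value for tables and figures as the "average of results for 3 days prior to the visit at home, both waking up and bedtime". For listings, "the value for using listing is the average of results for 3 days prior to the visit at home by waking up and bedtime". The contrast is plain: pooled for every summary and plot, separate only in the listing. Change from baseline is taken at each visit from the pooled value.

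SAP 7.5.3 describes the home readings as taken "both in the morning and in the afternoon". That does not match bedtime in SAP 7.5.3.2 or before bedtime in Protocol 5.1.5.

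On incomplete data, SAP 7.10.1 says "As a general principle, no imputation of missing data for other variables will be done". SAP 7.5.3.2 sets no minimum number of readings. It does not say how to handle unequal numbers of awakening and bedtime readings, or whether the average is a simple mean of all readings or a mean of the two time-of-day means. SAP 7.10 refers to a data specification document for further detail, which is not among the documents available.

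**The concern.** The protocol collects two readings a day that differ in their relation to dosing: one at the end of the dosing interval, one some hours after the dose. The summaries merge them. Home self-measurement is a named safety endpoint (Protocol 2.3.4), and pulse is not a routine variable here: "Identified risks with mirabegron treatment include increased heart rate and tachycardia as well as hypersensitivity reactions". Protocol 1.4.1.3 also lists increased blood pressure as a potential risk.

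The office summaries in SAP 7.5.3.1 do not fill the gap, because office readings have no specified time relative to the dose. The home readings are where a time-of-day pattern could be seen, and the planned tables and plots cannot show it. This includes the plot of maximum on-treatment value against baseline in SAP 7.5.3.2: it would use pooled visit averages, so a subject whose bedtime values alone rise would appear with half that rise.

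A second issue follows from the undefined average. If a subject's mix of awakening and bedtime readings changes between baseline and a later visit, ordinary variation over the day can enter the change from baseline. Gaps in the home readings are foreseen: footnote e to the Schedule of Assessments provides for discontinued subjects with no diary entry.

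**Working it through.** The documents state no figure for home vital signs, so there is none to reproduce. The check is algebra on the pooled average.

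**Inputs.** From Protocol 5.1.5: three awakening and three bedtime values per complete diary. Not in the documents, so shown over assumed ranges: f, the awakening effect as a fraction of the bedtime effect, from 0 to 1; and D, the bedtime-minus-awakening level, at 2, 5 and 10 units (bpm or mmHg).

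**1. Dilution with complete readings.** Let B be the treatment effect at bedtime and fB the effect at awakening.

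Pooled effect = (3·fB + 3·B)/6 = B(1 + f)/2

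| f | Pooled effect as share of bedtime effect |
|---|---|
| 0 | 50% |
| 0.25 | 62.5% |
| 0.5 | 75% |
| 0.75 | 87.5% |
| 1 | 100% |

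**2. Missing readings, if the average is a simple mean.** With m awakening readings at level L and e bedtime readings at level L + D:

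Mean = L + D·e/(m + e). For a complete diary this is L + 0.5D, so the shift is D·(e/(m + e) − 0.5).

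| Available (m + e) | Shift | D = 2 | D = 5 | D = 10 |
|---|---|---|---|---|
| 2 + 3 | +0.10D | 0.2 | 0.5 | 1.0 |
| 1 + 3 | +0.25D | 0.5 | 1.25 | 2.5 |
| 0 + 3 | +0.50D | 1.0 | 2.5 | 5.0 |

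Missing bedtime readings give the same sizes with a minus sign. These are shifts in one subject's value relative to a complete diary.

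**3. Missing readings, if the average is the mean of the two time-of-day means.** The value is (L + L + D)/2 = L + 0.5D whenever at least one reading exists at each time, so the shift from D is 0. A shift of 0.5D remains only if all readings at one time of day are missing and the other time is used alone.

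**4. Effect on the comparison between arms.** If shares p and q of the two arms lack all awakening readings after a complete baseline, the difference in mean change is distorted by (p − q)·0.5D. With p = q it is 0. With p = 10% and q = 5% it is 0.05 × 0.5D = 0.025D, which is 0.05, 0.125 and 0.25 units for D = 2, 5 and 10.

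**The case against.** The strongest reply is that these are descriptive summaries. Protocol 7.5.3 asks only for descriptive statistics by group and time point, and no test, threshold or decision uses the home average. Office readings are summarised separately, and cardiovascular, blood pressure and urinary retention events are of special interest (SAP 7.5.1.9). That stands, and it limits the weight of the point. It does not show that the pooled value is the better summary.

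A reader might infer several stronger things that the documents do not support:

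- **That pooling does dilute a drug effect.** On daily treatment the awakening reading follows the previous day's dose. It is pre-dose and at trough, but not drug-free. The documents give no time course of pulse or blood pressure effect at 50 mg, and the bedtime reading has no fixed interval after the dose. With equal effects at both times there is no dilution.
- **That a missing reading creates a false treatment difference.** It shifts a subject's change only if the two times differ in level and the mix differs from baseline. A single missing reading matters only under a simple mean, which the SAP does not specify. Equal missingness in the two arms cancels.
- **That the information is lost.** The listing keeps the two averages apart, and measurement and medication times are recorded.
- **That the protocol expects these risks to rise with exposure at the trial dose.** Protocol 1.4.1.3 ties the relation to supratherapeutic doses and names 50 mg as the maximum therapeutic dose.
- **That no averaging rule exists.** It may be in the data specification document. The definition of a named safety endpoint should still be readable in the SAP.

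**Conclusion.** The point holds in a limited form. The planned home tables, changes from baseline and plots merge a pre-dose trough reading with a post-dose reading, so they cannot show whether an effect differs by time of day. This follows directly from the text and needs no assumption.

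The size of any dilution does rest on an assumption. The pooled value lies between 50% and 100% of the bedtime effect for awakening effects between none and equal, and nothing in the documents places the trial within that range. The missing-reading shift of 0.1D to 0.5D in a subject's value depends on an unstated averaging rule and an unstated D. Its effect on the arm comparison needs unequal missingness and is small in the example shown.

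This is an improvement that should be made to a safety summary. It does not affect the primary analysis. The mismatch between afternoon and bedtime is a clerical error.

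**What to change.** - In SAP 7.5.3.2, tabulate and plot home SBP, DBP and pulse rate separately for awakening and bedtime, each with change from its own Visit 2 three-day mean.
- If a pooled value is kept, define it as the mean of the awakening mean and the bedtime mean, calculated only when both exist. This removes the shift from unequal numbers of readings.
- Reconcile the afternoon wording in SAP 7.5.3 with bedtime in SAP 7.5.3.2 and before bedtime in Protocol 5.1.5.

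The cost is SAP wording and a second set of descriptive safety tables and figures. No new data are needed, since the separate averages are already planned for the listing.

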7.5.4 Pregnancies

A detailed listing of all pregnancies will be provided.

7.5.5 Other Safety-Related Observations

The other safety endpoints are as follows:

- Post-void residual urine volume
- Qmax
- Average flow rate (Qave)

Concerning actual value and the change from baseline to post-baseline of the secondary endpoints, descriptive statistics will be calculated by treatment group at each visit and at the End of Treatment.

7.6 Analysis of PK

Not applicable to this study.

7.7 Analysis of PD

Not applicable to this study.

7.8 Subgroups of Interest

All efficacy endpoint and TEAEs will be summarized by the treatment group for the subgroups defined on the basis of the categorized variables listed below:

Grouping variable	Subgroups
Region*	Japan Korea
Age1	< 65 years ≥65 years
Age2	< 65 years ≥65 - < 75 years ≥75 years
BMI	< 25 kg/m ² ≥ 25 kg/m ²
Duration of the Primary Diagnosis**	<12months ≥12 months Unknown
Urgency Incontinence at Baseline	0 > 0
PVR	<Median ≥Median
Qmax	<15 ml/sec ≥15 ml/sec

*: For subgroup analysis for primary efficacy endpoint, “region” will be excluded from ANCOVA model.

** : If the month for diagnosis is missing and year of visit date of screening visit (Visit 1) – year of Diagnosis ≤ 1, then excluded from the subgroup analyses.

“Unknown” will be used only for demographic analysis, not used for subgroup analysis.

For more details refer to section [7.4.1.3](#), [7.4.4](#) and [7.5.1](#).

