6.3 Other Variables

The following variables will be derived for analysis:

- The duration of exposure in treatment period

For each subject, the Length of Time on study drug in treatment period will be calculated in days, using the following formula:

(‘Date of Last Study Drug Taken in Treatment period’[#] - ‘Date of First Study Drug Taken in Treatment period’[#]) + 1

#: These dates can be taken from [Date of Study Drug Taken-page of the Case Report Form]

- The duration of the primary diagnosis (unit: months)

Duration of the primary diagnosis (months) = 12 * (year of visit date of screening visit (Visit 1) – year of Diagnosis) + month of visit date of screening visit (Visit 1) – month of Diagnosis.

If the month for diagnosis is missing, then the month will be imputed by January. As a result, if the duration of primary diagnosis is less than 1 month, then it will be assumed to be 1 month.

If the month and year for diagnosis is missing, then duration of the primary diagnosis is missing.

- Percent overall compliance of the study drug (Mirabegron/Placebo) and Tamsulosin during treatment period

Overall compliance to the dosing schedule will be examined for subjects whose total tablet count of the study drug (Mirabegron/Placebo) and Tamsulosin is known.

Number of tablets which should have been taken depends on the duration of exposure because they should be taken as 1 tablet once daily after breakfast. The following formula can be used for both study drug (Mirabegron/Placebo) and Tamsulosin:

$$\frac{[\text{Total number of tablets consumed during treatment period}]}{[\text{The duration of exposure in treatment period}]} \times 100$$

Where, total number of tablets consumed will be calculated as:

(total number of tablets dispensed) – (total number of tablets returned) – (total number of tablets lost).

- Previous and concomitant medication

Previous medication is defined as medication with at least one dose taken before the date of the first dose of study drug in treatment period.

Concomitant medication is defined as medication with at least one dose taken between the date of first dose (inclusive) and the date of last dose (inclusive) of study drug in treatment period.

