7.4.1.3 Subgroup Analysis of Primary Endpoint

The analyses described in section 7.4.1.1 will be conducted by subgroups defined in section 7.8. The SAS code used to implement ANCOVA by subgroups will be similar to that shown below:

```
PROC GLM;  
  BY grouping variables;  
  CLASS treatment region;  
  MODEL chg = treatment region base / SS3;  
  LSMEANS treatment / ALPHA=0.05 CL PDIFF=CONTROL("PLACEBO + Tamsulosin");  
RUN;
```

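### SAP 7.8 drops men with a missing diagnosis month and a same-year diagnosis from the duration subgroups, although the SAP's own formula always puts them under 12 months

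*SAP*

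**What the plan says.** SAP 6.3 (Other Variables) derives duration in whole months: twelve times the difference between the Visit 1 year and the diagnosis year, plus the Visit 1 month, minus the diagnosis month. For partial dates it says "If the month for diagnosis is missing, then the month will be imputed by January", and adds that "if the duration of primary diagnosis is less than 1 month, then it will be assumed to be 1 month". Duration is set to missing when both month and year are missing.

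SAP 7.8 (Subgroups of Interest) lists the duration categories as "<12months ≥12 months Unknown". The footnote to that row opens "If the month for diagnosis is missing and year of visit date of screening visit (Visit 1" and, after the subtraction, ends "year of Diagnosis ≤ 1, then excluded from the subgroup analyses". A further note says that the Unknown category "will be used only for demographic analysis, not used for subgroup analysis".

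The subgroups are used in three places. For the primary endpoint, SAP 7.4.1.3 states "The analyses described in section 7.4.1.1 will be conducted by subgroups defined in section 7.8". SAP 7.4.4 summarises the continuous efficacy endpoints by subgroup, and SAP 7.5.1.6 does the same for TEAEs. SAP 7.2.3 also summarises duration as a continuous baseline variable and tabulates the duration groups.

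**The concern.** The visible purpose of the footnote is to keep out men whose side of the 12-month line cannot be known without the diagnosis month. A man diagnosed in the calendar year of his Visit 1 is not such a man: he cannot have reached 12 months. The footnote removes him anyway, and neither document gives a reason.

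The two SAP sections also sit awkwardly together. Section 6.3 gives this man a usable duration, which can enter the baseline summary of duration. Section 7.8 then treats the same information as too uncertain for a split that he cannot straddle. At stake is the needless loss of classifiable men from the under-12-month side of one prespecified subgroup variable.

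**Working it through.** The plan states no figure to reproduce here, so the check applies the SAP 6.3 formula to every possible month.

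**Inputs.** Let d be the Visit 1 year minus the diagnosis year, v the Visit 1 month (1 to 12) and m the unknown diagnosis month (1 to 12).
- Duration = 12d + v − m (SAP 6.3).
- With January imputed (m = 1), duration = 12d + v − 1, with a floor of 1 month (SAP 6.3).
- Cut-off: 12 months (SAP 7.8).
- Footnote exclusion: month missing and d ≤ 1 (SAP 7.8).
- Assumption: diagnosis does not follow Visit 1, so m ≤ v when d = 0. A later month would give a negative value, still below 12.

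**d = 0.** Duration = v − m. The largest value is 12 − 1 = 11 and the smallest is 0, which the floor raises to 1. There are 1 + 2 + … + 12 = 78 possible month pairs, and all 78 fall below 12. The January-imputed value, v − 1 with the floor, runs from 1 to 11 and gives the same class every time.

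**d = 1.** Duration = 12 + v − m, which for a given Visit 1 month runs from v to v + 11. It is below 12 when m > v, that is for 12 − v of the 12 possible months. Summed over v, that is 11 + 10 + … + 0 = 66 of 144 pairs. The January-imputed value is 11 + v, from 12 to 23, so imputation alone would place every such man at 12 months or more.

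**d = 2.** The smallest value is 24 + 1 − 12 = 13, so the class is certain; larger differences give longer durations.

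| Year difference | Visit 1 month | Possible duration (months) | Pairs under 12 | Class known without the month? | Excluded by footnote? |
|---|---|---|---|---|---|
| 0 | any | 1–11 | 78 of 78 | yes, <12 | yes |
| 1 | January | 1–12 | 11 of 12 | no | yes |
| 1 | June | 6–17 | 6 of 12 | no | yes |
| 1 | November | 11–22 | 1 of 12 | no | yes |
| 1 | December | 12–23 | 0 of 12 | yes, ≥12 | yes |
| 2 | any | 13–35 | 0 of 144 | yes, ≥12 | no |

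The 66 of 144 is a share of month combinations, not an estimate of the share of men.

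**Consistency with section 6.3.** Under January imputation the one-month floor operates only when 12d + v − 1 < 1, that is when d = 0 and v = 1. The floor in 6.3 therefore caters for exactly the kind of man, diagnosed in the same year with the month missing, whom the footnote in 7.8 excludes.

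**After the change.** With the exclusion limited to d = 1, all d = 0 men are classed under 12 months, with 0 of 78 month pairs misclassified. How many men this restores cannot be computed, because neither document counts missing diagnosis months.

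**The case against.** The strongest defence is that the rule is simple, prespecified and conservative: treating every recent diagnosis with a partial date as unclassifiable loses some information but puts nobody in the wrong group. It also matters little. It applies only when the year is recorded, the month is not, and the two years coincide. The dates that drive it precede randomization, so it cannot depend on assigned arm. Protocol 7.4.1.3 names only region and baseline urgency incontinence as subgroups; duration was added in the SAP, and no decision rests on it. All of this stands and fixes the size of the point. It does not supply a reason to discard men whose class is certain.

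Three stronger readings may tempt a reader, and the documents do not support them.

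- That the rule as a whole is one-sided and can only shrink the under-12-month group. It also removes men with a difference of 1, all of whom January imputation would have put at 12 months or more. Only the unnecessary same-year part falls solely on the under-12-month group.
- That the under-12-month group is already the smaller one. Neither document gives a distribution of disease duration.
- That the men excluded by the footnote are those counted as Unknown in the demographic table. SAP 7.8 says where Unknown is used, not who is in it. Men with both month and year missing could be its only source, and SAP 7.10 defers further data-handling detail to a data specification that is not part of these documents.

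**Conclusion.** The point holds as a small error in a stated rule. At a year difference of 0 the footnote excludes men whom the SAP's own formula places under 12 months in every possible case. Excluding men at a difference of 1 is justified for a Visit 1 from January to November and unnecessary for one in December.

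The consequence is limited to the duration rows of the subgroup ANCOVA for the primary endpoint, the efficacy summaries and the TEAE tables. The number of men affected is unknown and may be zero. The comparison between arms within the subgroup is not biased by the rule. The primary ANCOVA, the FAS, the sample size and the overall safety totals are unaffected. The conclusion assumes that the recorded diagnosis year is correct and that the footnote, attached to the duration row, governs the duration subgroups only.

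**What to change.** In the SAP 7.8 footnote, change the condition from a year difference of 1 or less to a difference equal to 1, and state that a difference of 0 with a missing month is classed as under 12 months. Optionally, also class a difference of 1 with a December Visit 1 as 12 months or more; the exclusion then covers exactly the men whose class is undetermined.

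State in SAP 7.2.3 or 7.8 that the demographic duration grouping uses the same classification, and say which men make up the Unknown category.

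The cost is one comparison operator and a sentence or two in the SAP, with the matching line in the derivation program. No new data are needed and no misclassification is introduced. The change should be made before unblinding; if the SAP is already final, SAP section 1 requires changes to the planned analyses to be justified in the Clinical Study Report.
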